Despite the known effectiveness of buprenorphine sublingual (BSL) maintenance treatment, retention and continued non-prescribed opioid use remain significant limitations. Two recent large trials comparing BSL to other OUD pharmacotherapies found that around 50% or more of patients treated with BSL dropped out of treatment by 3 to 6 months. The first long-acting injectable buprenorphine (Sublocade™) became commercially available in 2018 after receiving an FDA Fast Track and Priority Review designation. This monthly buprenorphine formulation, which is available in two doses (100 mg and 300 mg), can achieve serum buprenorphine concentrations in excess of that achieved by BSL 24 mg per day. Moreover, if an unexpected drug holiday is experienced, at two weeks past the injection due date, μ -opioid receptor remains above 70%, providing some measure of protection against relapse to opioid use. While the Sublocade™ buprenorphine extended-release (BXR) injection product has not yet been compared to BSL treatment for the treatment of OUD, the pharmacologic advantages of BXR can be expected to improve treatment retention and outcome. The extended-release injection aspect should improve compliance and reduce relapse by providing more continuous buprenorphine serum levels as compared to the sublingual formulation. We hypothesize that the BXR injection will have particular benefit for individuals using fentanyl analogues and other HPSO because by providing continuous therapeutic serum buprenorphine levels there will be substantially less opportunity for non-compliance and relapse. Even in the case of a delayed injection, therapeutic levels of buprenorphine will be present for up to two weeks.

We propose an open-label, uncontrolled pilot study, in which patients seeking treatment for OUD who are positive for fentanyl analogues at screening (N = 10) will be inducted onto BSL and then receive BXR injection, with a primary outcome comparison of end of study opioid use compared to baseline. To our knowledge, this would be the first trial to examine the use of this BXR injection formulation for the treatment of OUD patients positive for fentanyl analogues, and the first pharmacotherapy trial of any agent for the treatment of patients with OUD testing positive for HPSO.

Specific Aims and Hypotheses

Specific Aims and Hypotheses

Aim 1: To determine if BXR injection using standard dosing is a feasible treatment for patients with OUD who are positive for HPSO.

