Primary Hypothesis: BXR treatment will be associated with decreased opioid use for OUD patients positive for HPSO. The primary outcome measure will be opioid use during the last two weeks of the study compared to baseline as measured by a combination of urine toxicology and self-report.

Secondary Hypotheses: BXR injection will be associated with reduce symptoms of craving and symptoms of withdrawal as compared to baseline.

If found promising, the results of this pilot trial would support advancement of conducting a controlled trial, with the potential to improve the effectiveness of OUD pharmacotherapy for this subgroup more vulnerable to fatal overdose.

Description of Subject Population

Sample #1

Specify subject population

Adults with OUD testing positive for HPSO

Number of completers required to accomplish study aims

5

Projected number of subjects who will be enrolled to obtain required number of completers

10

Age range of subject population

18-65

Gender, Racial and Ethnic Breakdown

We plan to enroll 10 participants into the study. Both males and females will be recruited. All eligible participants are accepted; however, past experience with recruitment for opioid use disorders suggests that the approximate gender distribution for this study will likely be 20% female and 80% male. Previous and ongoing opiate studies at STARS have had samples comprised of approximately 50% Caucasians, and 50% ethnic minorities distributed as 24% African-American and 22% Hispanic-American, and 4% other. We anticipate a similar representation in this project. We will make every effort to recruit minority patients in order to ensure the generalizability of our findings to the overall treatment population.

Description of subject population

Prospective subjects will be 10 men or non-pregnant women of any ethnicity or race, aged 18-65. Enrolled

subjects will be individuals with OUD who test positive for HPSO.

Recruitment Procedures

Describe settings where recruitment will occur

The project will be completed at the Substance Treatment and Research Services (STARS downtown) situated on [name].

How and by whom will subjects be approached and/or recruited?

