Will subjects in this study participate in or be recruited from other studies?

Yes

Describe concurrent research involvement

Screening for this study will be covered by the Substance Treatment and Research Service (STARS) umbrella screening protocol #6582R (PI: [name]). Trained research assistants and administrative assistants under the supervision of the principal investigator conduct the initial phone screening. Under protocol #6582R, patients who contact STARS interested in research trial participation are informed that they will be asked questions of a personal nature and asked to provide verbal consent for such questions. A "phone screen" form is completed by the phone screener, which asks basic demographic information, contact information (for scheduling purposes) and description of substance use to determine whether an in-person evaluation appointment is appropriate. Individuals are also informed that if they make an initial screening appointment this "phone screen" information will be forwarded to the clinician to facilitate the first meeting.

Inclusion/Exclusion Criteria

Name the subject group/sub sample

Adults with OUD

Create or insert table to describe the inclusion criteria and methods to ascertain them

1. Individuals between the ages of 18-65	1. legal identification
2. Voluntarily seeking treatment for opioid use	2. self-report
3. Meets current DSM-5 criteria for OUD as a primary diagnosis, with at least moderate severity	3. clinical interviews; MINI assessment
4. Test positive for HPSO use	4. urine toxicology
5. Able to provide informed consent and comply with study procedures	5. clinical assessment, MMSE (individuals over 60 years old)

Create or insert table to describe the exclusion criteria and methods to ascertain them

1. Meets DSM-5 criteria for substance use disorder other than opioid as the primary diagnosis	1. clinical interviews
2. Having a comorbid psychiatric diagnosis that might interfere with participation or make participation hazardous, such as an active psychotic disorder or current suicide risk	2. clinical interviews
3. Methadone maintenance treatment	3. self-report; urine toxicology
4. Buprenorphine maintenance treatment	4. self-report; urine toxicology
5. Known history of allergy, intolerance, or hypersensitivity to candidate medication (buprenorphine)	5. clinical assessment,

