The MINI International Neuropsychiatric Interview (MINI): will be performed during screening as part of a complete psychiatric diagnostic assessment.

Medical Screening and Evaluation: Medical examination and laboratory work will follow consent. ECGs, blood draws, and urinalyses will be obtained by a lab technician. All tests are conducted using accepted clinical techniques and samples (e.g. bloods) are collected using universal precautions. Pregnancy tests will be conducted for women. A Health Survey will be conducted with special attention devoted to cardiovascular function. A cardiologist is available for STARS participants and will review any abnormal ECGs, and determine whether or not a patient can be safely enrolled in the trial.

Physiological Measures:

- *Medical History and Physical Exam:* A comprehensive medical history and physical examination will be performed during the screening process.
- *Pregnancy Testing:* Serum pregnancy testing will be performed on all females during screening and urine pregnancy tests will be performed at baseline and weeks 4, 8, and 12
- *Serum laboratory examination:* Complete blood count, electrolyte, and liver function tests will be performed during the screening process and follow up at weeks 4, 8, and 12
- *Urinalysis:* Laboratory urinalysis (glucose, protein, ketones, pH, specific gravity, and microscopic analysis) will be performed during the screening process and follow up at weeks 4, 8, and 12
- *Urine Toxicology:* Urine samples will be collected during screening and a full urine toxicology will be tested and at each study visit during the trial. Participants will provide urine twice weekly
- *Electrocardiogram (ECG):* will be completed at baseline
- *Vital Signs and weight/BMI:* Temperature, pulse, blood pressure, and weight with calculated BMI will be measured at each visit for data collection and safety monitoring purposes.

Medication and rationale:

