Urine Drug Testing: A urine sample will be collected at each visit (daily during the first week and twice-weekly during weeks 2-12). Each sample will be tested for naturally occurring (e.g., morphine, heroin), semi-synthetic opioids, and buprenorphine. HPSO will be tested for once weekly due to expense.

Assessment Instruments

Create a table or give a brief description of the instruments that will be used for assessment

Assessment of Drug Abuse Severity

Clinical Global Impression Scales for Substance Abuse: This is a clinician-rated and self-rated instrument that rates global severity and improvement on 7-point scales for opioid use. On the improvement scale a rating of 1 = "very much improved" requires abstinence, and a rating of 2 = "much improved" requires at least a 75% reduction in substance use since beginning study medication. The opioid change score is dichotomized such that patients scoring 1 or 2 are rated "responders" and all others "non-responders." A similar approach will be used to assess severity and improvement for global symptoms weekly by the study physician.

Timeline Follow-back (TLFB) Assessment: The Timeline Follow-Back method will gather self-reported opioid use data for each day during the 28 days prior to study enrollment and each day during the study period. Other substance (including nicotine and alcohol) use self-report data will also be gathered during the TLFB interview.

Urine Drug Testing: A urine sample will be collected under direct observation at each visit (twice-weekly). Each sample will be tested for naturally occurring (e.g., morphine, heroin), semi-synthetic opioids, and buprenorphine. HPSO will be tested for once weekly due to expense.

Craving Visual Analog Scale: A visual analog scale is used for patients to rate the intensity of craving for opioids experienced since the previous visit (Bisaga et al., 2011).

Clinical Opiate Withdrawal Scale (COWS): The COWS is a 11-item scale reliably eliciting severity of common physical and psychological symptoms of opiate withdrawal (Wesson, 2003). It will be used to examine occurrence of symptoms of opioid withdrawal and will be collected at each visit.

Miscellaneous Measures

Hamilton Depression Scale (HAM-D): In addition to mood symptoms, the HAM-D has items that measure anxiety, low appetite, irritability, and insomnia, which are symptoms of subacute opioid withdrawal of particular interest for this study (Hamilton 1960).

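### Could an HPSO-positive entry urine and once-weekly HPSO testing create a false fall in the opioid-use outcome?

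*Protocol*

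**What the plan says.** The Protocol (Specific Aims and Hypotheses) defines the outcome as "opioid use during the last two weeks of the study compared to baseline as measured by a combination of urine toxicology and self-report". SAP C3 repeats this under Secondary Outcomes and names the proportion successfully inducted onto BXR as the Primary Outcome.

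On entry, the Background describes patients "who are positive for fentanyl analogues at screening (N = 10) will be inducted onto BSL", and inclusion criterion 4 reads "Test positive for HPSO use".

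On urine testing, Blood and other Biological Samples sets collection as "daily during the first week and twice-weekly during weeks 2-12". For the assays it says "Each sample will be tested for naturally occurring (e.g., morphine, heroin), semi-synthetic opioids, and buprenorphine", followed by "HPSO will be tested for once weekly due to expense". Assessment Instruments repeats both assay statements. The Physiological Measures list has a looser sentence: "Urine samples will be collected during screening and a full urine toxicology will be tested and at each study visit during the trial".

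On self-report, the Timeline Follow-back (TLFB) gathers "self-reported opioid use data for each day during the 28 days prior to study enrollment and each day during the study period". The COWS is collected at each visit.

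The supplied text does not name the baseline urine, the rule for combining urine with self-report, the scoring of a urine not assayed for HPSO, or the baseline COWS value. The Protocol refers to a separate table of study assessments for full detail; that table is not in the file.

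**The concern.** HPSO use defines this population, yet fewer than half of the study urines would be assayed for it. Two routes to a spurious improvement suggest themselves.

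1. **Selection.** If the qualifying urine is also the baseline, HPSO status starts at 100% and can only fall. With intermittent positivity, some participants turn negative without any change in use.
2. **Scoring.** If the two end-of-study urines without an HPSO assay count as opioid-negative, unchanged HPSO use looks smaller.

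There is a parallel question about withdrawal. Participants start sublingual induction in withdrawal (COWS > 6) and are injected on day 4, while the hypothesis credits the injection. A pre-induction baseline would fold the induction effect into the injection effect.

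With 10 participants and no control arm, nothing else in the design would expose such an artefact, and the Protocol says promising results would support a controlled trial.

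**Working it through.** **Inputs from the documents**
- Visits, inferred from the payment cap in Compensation: 270 / 10 = 27. Weeks 2-12: 11 x 2 = 22. Week 1: 27 - 22 = 5.
- HPSO assays at one per week: 12 of 27 urines (12/27 = 44%). Week 1: 1 of 5. Weeks 11-12: 2 of 4, at full attendance.
- N = 10; completers required = 5.

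The plan gives no effect size or power figure to reproduce.

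**Assumed inputs.** Let p be the share of urines truly HPSO-positive, unchanged through the study. Let o be the share of those that the routine panel also flags. Neither is in the documents. The Background's figure of nearly 80% is a rate across patients, not across one patient's urines.

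**Route 2: untested urines scored negative.** Let c be the share of urines assayed for HPSO at a time point. The share scored positive because of HPSO use is c x p + (1 - c) x p x o. Urines positive only for other opioids contribute equally at both time points and cancel. With no true change:

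end minus baseline = (c_end - c_base) x p x (1 - o), with c_end = 2/4 = 0.5.

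| Baseline | c_base | Apparent change | p = 0.8, o = 0 | p = 0.8, o = 0.5 |
|---|---|---|---|---|
| Fully HPSO-assayed | 1 | -0.5 x p x (1 - o) | 40-point fall | 20-point fall |
| Week 1 | 1/5 = 0.2 | +0.3 x p x (1 - o) | 24-point rise | 12-point rise |
| Pre-dose urine, no HPSO assay | 0 | +0.5 x p x (1 - o) | 40-point rise | 20-point rise |
| HPSO scored on assayed urines only, both times | same coverage | 0 | 0 | 0 |

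The sign therefore depends on a baseline the text does not name. A fall appears only if the baseline is more completely assayed than the end of study.

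**Route 1: the eligibility urine as baseline.** With within-patient correlation rho and one later test, the expected number of 10 turning HPSO-negative is 10 x (1 - p) x (1 - rho).
- p = 0.8: 2.0, 1.0 and 0 for rho = 0, 0.5 and 1.
- p = 0.5: 5.0, 2.5 and 0.

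These counts concern HPSO status. The named outcome is opioid use. Participants have OUD of at least moderate severity and are in withdrawal when induction starts, so they are active users. A urine that is HPSO-negative but positive on the routine panel is still opioid-positive, which shrinks this effect. A separate pre-dose baseline is also possible: Physiological Measures has urine pregnancy tests at baseline, and there is a clinic visit before the first sublingual dose.

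**Self-report.** The TLFB covers every study day, including days with no HPSO assay. The Background says patients often do not know they have taken fentanyl analogs, but it says this of patients who report heroin use. Their TLFB would still record opioid use. Since no combination rule is stated, the net effect on the combined outcome cannot be computed.

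**COWS.** Because it is taken at each visit, both the pre-induction and the last pre-injection values should be on file for whichever contrast is reported.

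**Testing frequency.** The Physiological Measures sentence on full toxicology is ambiguous about study visits. Once-weekly HPSO testing is explicit and stated twice, so it is the natural reading.

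**The case for a change.** The best case for a change is that the SAP should fix scoring before data are seen, and that both artefacts, as posed, favour the treatment. The illustration can look serious. Take an exact two-sided sign test (my assumption; the SAP names none) with N = 10, p = 0.8 and no true change. The eligibility baseline falsely shows a decrease in about 11% of trials. Untested-as-negative scoring against an HPSO-assayed baseline does so in 32-40% (o = 0.5 and 0). An unselected baseline with only assayed urines scored gives about 1%. The wording needed would be short, and the missing assessment table probably would not supply a scoring rule.

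What stands is that the baseline urine, the combination rule, the treatment of untested urines and the baseline COWS value are unstated, and writing them down would be good practice. What does not stand is the step from silence to a biased result. The percentages rest on assumed p and o, on independent tests, on HPSO-driven scoring without self-report, and on scoring choices found nowhere in the text. With only the 5 required completers, the smallest two-sided sign-test p-value is 2 x 0.5^5 = 0.0625, so a spurious fall could affect the estimate but could not reach 0.05. The obvious substitute baseline, a pre-dose urine, follows an instruction to abstain and may understate usual use, so changing the baseline is not free of bias either.

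**Conclusion.** No change to the plan follows. Assaying HPSO weekly on grounds of cost is a fair trade-off, and it still gives two HPSO results per participant in the outcome window. The remaining gap is one analysts fill sensibly: a urine not assayed for HPSO is not tested for HPSO, and an entry-criterion result is not an unselected baseline. Under that handling the urine artefact is zero.

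Under the least sensible handling (p = 0.8, o = 0), the scoring artefact runs from a 40-point fall to a 40-point rise depending on the baseline, so no direction of bias can be attributed to the plan. These sizes assume unchanged use, full attendance, and values of p and o that the documents do not give. Daily TLFB may offset them to an unknown degree. The results come from a 10-patient uncontrolled pilot, whose pre-post comparison no urine rule would make confirmatory. The differing primary-outcome labels in the Protocol and the SAP are a separate matter and do not affect this conclusion.

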
The proposed study is a 12-week, open-label pilot study of sublocade (extended-release buprenorphine, BXR) as treatment for opiate use disorder (OUD) testing positive for Highly Potent Synthetic Opioids (HPSO). We plan to enroll 10 participants into the study. Outpatients seeking treatment for OUD will be screened, and those eligible and consenting will be inducted onto sublingual buprenorphine (target dose 16mg to 24mg). On the fourth day after starting the buprenorphine induction, participants will receive BXR 300mg by subcutaneous injection. Participants will be seen twice per week for urine collection for toxicology and research assessments and will have Medication Management counseling weekly during one of these visits. BXR will be administered monthly and dosing will be according to the FDA prescribing instructions of 300mg for the second dose and 100mg for the third. The aim of this study is to determine if BXR injection using standard dosing is a feasible treatment for patients with OUD who are positive for HPSO.

Background, Significance and Rationale

Background, Significance and Rationale

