Discharge and aftercare planning and implementation will be incorporated into the study. Participants will be given appropriate referrals when the study is completed and will be offered 4 weeks of continued meetings with the physician in order to facilitate transition and permit overlap with another treatment program for aftercare. Discussion of treatment recommendations as well as risks and benefits of accepting and refusing referrals will take place and will be documented.

Participants will be offered to be transferred back to sublingual buprenorphine with clinical dosing during the 4 weeks of continued aftercare with the research physician. This discussion and decision, along with ongoing meetings with the physician will be documented in the clinical chart.

Clinical Treatment Alternatives

Clinical treatment alternatives

Participants will be informed of alternatives to participation in the proposed trial, including referrals in the community, residential or inpatient, or medical treatment.

Alternative Treatments and Procedures: The primary effective treatments for OUD are buprenorphine, methadone and XR-NTX. The effectiveness of standard OUD pharmacotherapy for individuals with OUD positive for HPSO is unknown. Participants of the proposed study will receive an evidenced-based treatment for OUD, although clinical trial participation is a more restricted treatment environment than community-based clinical treatment. Several psychotherapy methods have been shown to be effective in augmenting OUD pharmacotherapy and include: Relapse Prevention Therapy, a form of CBT; Contingency Management, a prize- or voucher-based incentive treatment; Motivational Enhancement Therapy (MET), a form of Motivational Interviewing; the combination of CBT and MET together; and family therapy. During the study, participants are permitted to seek additional help from other providers (therapists and physicians outside of the study) which will be tracked using the modified treatment services review. Patients are informed that they may request referral for other treatment options and if a participant's condition worsen (see trial exit criteria), participants will be referred for clinical treatment.

Risks/Discomforts/Inconveniences

Risks that could be encountered during the study period

Potential risks

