In order to minimize the risk associated with the study, subjects undergo a comprehensive medical and psychiatric evaluation during the screening procedure. The baseline medical evaluation consists of a physical examination, blood chemistry profile (including liver function tests), complete blood count, urinalysis, serum pregnancy test, urine toxicology and is designed, along with the clinical history, to detect chronic and/or unstable medical illnesses. A comprehensive psychiatric assessment is performed during the screening process, and is intended to detect and assess all past and current psychiatric disorders. The eligibility criteria (see above) are designed to minimize the medical and psychiatric risks to participants by excluding those for whom participation would place them at an increased risk. Special attention will be given to patient's concurrent use of medications. Participants on medications that meet exclusion criteria will not be included in the study.

2) Study Procedures

Participants will be informed about the possible side effects and risks (listed above) of taking BXR or BSL both alone and in combination with other medications, alcohol, or illicit drugs through extensive discussions with staff psychiatrist(s) during the consent process. Participants will be monitored closely with urine drug tests and collecting use episodes each time they attend the clinic. If relapse occurs participants will be given referrals for methadone, buprenorphine maintenance, or inpatient detoxification and follow-up treatment if deemed necessary.

Participants will be told to contact the clinic if they experience any adverse effects and given the number for the 24-hr physician on-call. All participants, both those not taking and taking concurrent medications, will be monitored closely throughout the study for possible signs and symptoms of intoxication and potential for medication misuse. Participants' mental status and physical health are monitored weekly during the study period by a psychiatrist. Vital signs will be obtained at each study visit. At clinic visits, a physician will assess participants for signs and symptoms of adverse effects of buprenorphine, noting which if any symptoms are present, the severity of the symptoms, make adjustments to study medication dose, discontinue study medication, or withdraw participant(s) from the study if needed.

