Study: # 7764 entitled An Open-Label Pilot Study of Sublocade as Treatment for Opiate Use Disorder

PI: [name]
NCT# NCT03861338
Data Analysis Plan created 2-25-2019

C. DATA MANAGEMENT AND ANALYSIS

C1. Data Acquisition and Transmission

All data will be obtained specifically for research purposes. Data will be entered into an Excel spreadsheet coded with a unique identifier assigned to each participant. Departmental, HIPAA-compliant Research Subject Registration System, will however contain participants' names.

C2. Data Entry Methods

As noted above, data will be entered into an Excel spreadsheet. Data management will include: 1) protocol management; 2) patient scheduling; 3) regulatory reporting and 4) management of research organizations, personnel, and collaborators. The research staff will collect and input data on a daily, basis to reduce the likelihood of errors. Information collection and analysis and study-specific data collection will be easily retrievable, organized, and reviewed on an ongoing basis as well.

C3. Data Analysis Plan

Overview of Data Analytic Plan

Sample size: A total of 10 participants will be recruited.

A total of 10 patients will be recruited over a 6-month period. The main analyses in this study will be on the intent-to-treat (ITT) sample, i.e. on all enrolled patients who receive study medication, and all tests will be two-sided, performed at significance $\alpha=0.05$, except where noted. Before specific statistical techniques are applied in order to test the hypotheses of interest, we will examine all variables at all time points for outliers. The distributions of all continuous variables will be checked for normality, and transformations will be employed, if necessary, before applying specific parametric techniques.

Hypotheses testing:

Primary Outcome: The proportion of participants successfully inducted onto BXR.

Secondary Outcomes: BXR treatment will be associated with decreased opioid use for OUD patients positive for HPSO. The primary outcome measure will be opioid use during the last two weeks of the study compared to baseline as measured by a combination of urine toxicology and self-report. BXR injection will be associated with reduce symptoms of craving and symptoms of withdrawal as compared to baseline.

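### The analysis of opioid use in the last two weeks does not separate use measured on BXR from use measured after a relapse-driven switch to another treatment

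*Protocol*

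**What the plan says.** **Other treatment during the study.** The Protocol, in its procedures for minimizing risks (item 2, Study Procedures), says: "If relapse occurs participants will be given referrals for methadone, buprenorphine maintenance, or inpatient detoxification and follow-up treatment if deemed necessary". Its Clinical Treatment Alternatives section also allows care from elsewhere while the trial runs: "participants are permitted to seek additional help from other providers (therapists and physicians outside of the study"). Such outside care is to be recorded with a modified treatment services review. Methadone and buprenorphine maintenance appear among the exclusion criteria, so they bar entry. Neither document gives an analysis rule for starting either one later.

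**The outcome.** The SAP (C3, Hypotheses testing) says: "The primary outcome measure will be opioid use during the last two weeks of the study compared to baseline", by urine toxicology combined with self-report. The Protocol's Specific Aims and Hypotheses section has the same measure as its primary outcome. The SAP places it under another label, "Secondary Outcomes: BXR treatment will be associated with decreased opioid use for OUD patients positive for HPSO", and names a different primary: "Primary Outcome: The proportion of participants successfully inducted onto BXR".

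**The analysis set.** The SAP's main analyses are intent-to-treat, "on all enrolled patients who receive study medication". No exception or alternative scoring is given for a participant who changes treatment.

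**The design.** The Lay Summary begins: "The proposed study is a 12-week, open-label pilot study". The last two weeks are therefore weeks 11 and 12. There is no control arm.

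**The concern.** The hypothesis is about BXR itself: that treatment with it goes with less opioid use. The measure is a snapshot at the end of the study. Suppose a participant relapses on BXR in week 6, is referred, starts methadone, keeps attending and reports no illicit use in weeks 11 and 12. The course on BXR was a failure, yet the snapshot shows a reduction from baseline. An inpatient stay in those weeks raises the same problem, because days without use may reflect the setting.

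With no comparator, nothing shows how much of the overall reduction came from other treatments. The Protocol says the pilot, if promising, would support a controlled trial, so a flattering response figure would carry forward into that decision. The information needed to separate these cases is to be collected through the treatment services review, but no analysis uses it.

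**Working it through.** **1. The plan's own figure.** The Protocol's subject-population section gives 5 completers required and 10 to be enrolled. That implies 50% completion: 5 / (1 − 0.50) = 10, which reproduces the stated number. The plan states no dropout assumption for this purpose, and no power, effect size or success rate for the opioid-use outcome. There is nothing further to reproduce.

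**2. Can a switched participant have weeks 11-12 data?**
- Referral after relapse is conditional on need.
- Under Criteria for Early Discontinuation, worsening that calls for more intensive treatment permits removal but does not require it. Continued use that puts the participant at significant risk does lead to discontinuation. Some relapsers can therefore stay and others will leave.
- For those who stay, the Timeline Follow-Back (TLFB) covers every study day and urine is collected twice weekly. Their weeks 11-12 data will exist and enter the analysis.
- Those who leave are asked back for a final appointment to check health and to finish interviews and paperwork already started. The text gives no date for it and mentions neither urine nor a weeks 11-12 TLFB. Many of these participants will have missing data, for which the SAP also has no rule.

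**3. Size per participant.** Assume a per-participant improved/not-improved outcome; the SAP defines none. With m evaluable, one reclassified participant moves the proportion by 100/m points. For m = 10 this is 10 points; for m = 5 it is 20.

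The documents do not give the number of rescued participants. On an assumed range of 0 to 5 out of 10, the shift is 0 to 50 points.

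**4. Illustration of consequence.** The SAP names no test, so a two-sided exact sign test is assumed, with n = 10 and no ties: p = 2 × P(X ≥ x), X ~ Binomial(10, 0.5). Intervals are Clopper-Pearson.

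| Improved | 95% interval | p |
|---|---|---|
| 10/10 | 69.2% to 100% | 2 × 1/1024 = 0.002 |
| 9/10 | 55.5% to 99.7% | 2 × (10+1)/1024 = 0.021 |
| 8/10 | 44.4% to 97.5% | 2 × (45+10+1)/1024 = 0.109 |
| 7/10 | 34.8% to 93.3% | 2 × (120+45+10+1)/1024 = 0.344 |

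If one of nine improvers improved only after a switch, the result moves from 9/10 to 8/10 and crosses 0.05. Among single-participant steps in this table, no other does so. With five evaluable, the smallest attainable p is 2 × 1/32 = 0.0625, so no crossing is possible.

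**5. Can urine identify switchers?** Each sample is tested for buprenorphine, which BXR itself supplies, so a positive result does not reveal outside buprenorphine. The per-sample panel in the Urine Drug Testing text does not name methadone, although the screening description refers to full toxicology. No rule classifies either drug when prescribed. The treatment services review is therefore the workable source for identifying switches.

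**The case against.** The strongest reply is that analysing all observed data, whatever treatment followed, is a recognised intent-to-treat strategy. Scoring a switch as non-response is one alternative among several. That is fair, and an explicit choice of the as-observed analysis would be defensible. But the SAP makes no explicit choice, and the hypothesis concerns BXR itself, not a policy of starting BXR and referring on.

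Four further points limit the concern.
- **Missing data.** Referral after relapse will often coincide with leaving the study, so part of the problem is absent data. This stands for leavers, but not for relapsers who remain in follow-up.
- **Direction.** A reader might infer that the bias can only favour BXR. The documents do not support this. Prescribed methadone or outside buprenorphine, if read as opioid-positive, would count against BXR. The outcome is also change from baseline, so a participant who lapsed may already have been below baseline before switching.
- **Carry-over.** Post-switch data need not reflect the new treatment alone. Injections fall on about days 4, 32 and 60. Someone who switches in week 6 after the day-32 dose has the next dose due on day 60. The Protocol's background claims effect for two weeks past the due date, to about day 74, which lies in week 11 (days 71 to 77). This blurs attribution but does not make the relapse a BXR success.
- **Status.** This is a ten-person feasibility pilot, and the SAP's primary outcome is induction, which later treatment cannot change. This lowers the stakes. The opioid-use measure is nevertheless the Protocol's primary outcome.

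**Conclusion.** The concern holds in limited form. The analysis as written does not distinguish opioid use on BXR from use measured after a relapse-driven switch. A participant who relapses, switches, stays in follow-up and stops using would support the BXR hypothesis. Each one is worth 10 percentage points if all 10 are evaluable. The number is unknown, and some switchers will have no weeks 11-12 data.

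Two stronger readings go too far. A reader might infer that the plan expressly scores rescue as BXR success. No sentence says so; the result follows from the analysis set together with silence on switching. A reader might also infer that one switcher would overturn the trial's conclusion. That needs the assumed sign test, ten evaluable participants and exactly nine improvers, none of which the plan specifies.

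The change is worth making before analysis, because the as-written snapshot answers the BXR question less well than an easily available alternative.

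**What to change.** Leave referral practice as it is and add the following to SAP section C3 for the opioid-use outcome.

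1. Define improved for an individual participant.
2. Count as not improved anyone who, because of relapse or continued opioid use, starts another medication for opioid use disorder or enters inpatient or residential treatment after first study medication and before the end of week 12. Report the as-observed intent-to-treat result alongside.
3. Handle switches for other reasons separately and list them. One example is exit for pregnancy, where the Protocol offers methadone or buprenorphine without any relapse.
4. Exclude controlled-environment days from both numerator and denominator of TLFB use days.
5. Do not count prescribed methadone or buprenorphine in urine as illicit opioid use.
6. Report the number of switchers, with reasons, from the treatment services review. Ask early leavers about other treatment at their final appointment, since the Protocol describes tracking only during the study.

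The cost is a short SAP paragraph and one added question for early leavers. The response figure will be somewhat less favourable, but the as-observed figure remains available beside it. The SAP's induction outcome needs no change.
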